9.3 RANDOMIZATION PROCEDURES

All ARDS criteria must occur within the same 24 hour period. The onset of ARDS is when the last criterion is met. Patients must be enrolled within 168 hours of ARDS onset. Information for determining when these time window criteria were met may come from either the site hospital or reports from a referring hospital.

Following randomization, the low tidal volume protocol for mechanical ventilation must be initiated within two hours.

The first treatment of study drug should be given within 24 hours of randomization. The day of randomization will be considered study day zero.

Eligible participants will be randomized to one of the two treatment arms using a permuted block method¹⁵¹ with random block sizes. The randomization ratio will be 1:1 iCO:placebo. The randomization will not be stratified by any factors. The study biostatistician will verify all the necessary randomization information (blinding method, randomization method, block size, and number of treatment groups) in the StudyTRAX randomization configuration module.

Site investigators will review all potential study participants with one of the DCC physician members. Following informed consent, the unblinded administering RT or physician or blinded study coordinator will randomize subjects in the database using the StudyTRAX randomization tool. The unblinded administering RT or physician will obtain the subject's treatment assignment through the "View Treatment" button in the blinded database, a privilege granted to unblinded RTs and physicians only. CO-related measurements (SpCO, COHb, ambient CO) and drug-related information will be in a separate project within the database, which the blinded study

coordinators will not have access to. This central review of randomization by the DCC unblinded physician will ensure that no subjects are enrolled in this multi-center trial during planned or unplanned study holds.

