7.3 MEASURES TO MINIMIZE BIAS: RANDOMIZATION AND BLINDING

Eligible participants will be randomized to one of the two treatment arms using a permuted block method¹⁵¹ with random block sizes. The randomization ratio will be 1:1 iCO:placebo. The randomization will not be stratified by any factors. The study biostatistician will verify all the necessary randomization information (blinding method, randomization method, block size, and number of treatment groups) in the StudyTRAX randomization configuration module.

Site investigators will review all potential study participants with one of the Data Coordinating Center (DCC) physician members. Following informed consent, the unblinded administering RT or physician or blinded study coordinator will randomize subjects in the database using the StudyTRAX randomization tool. The unblinded administering RT or physician will obtain the subject's treatment assignment through the "View Treatment" button in the blinded database, a privilege granted to unblinded RTs and physicians only. CO-related measurements (SpCO, COHb, ambient CO) and drug-related information will be in a separate project within the database, which the blinded study coordinators will not have access to. Permission to this limited-access project will only be granted to unblinded study personnel by the PI, as it contains treatment-specific information such as CO monitoring and study drug administration data.

The study drug assignment will be blinded to the subject, clinical team, study coordinators, and other study staff with the exception of the administering study staff (RT and physician OR physician alone), who will be unblinded to the treatment assignment to ensure subject safety. We chose this partially double-blind design to ensure safe iCO administration and an unblinded assessment of COHb levels in order not to exceed potentially toxic thresholds.

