To maintain blinding, the placebo gas cylinders are identical in appearance as the CO cylinders (with the exception of different CGA valves required by the manufacturer Praxair). Cylinders will also be shrouded in dark sleeves to ensure blinding. The placebo gas will be administered via inhalation via the CoventDS and delivered to subjects in an identical fashion as those randomized to CO. To ensure that the subject, study coordinator, and clinical staff remain blinded to the study drug assignment, the administering RT and physician study staff member OR physician study staff member alone will conceal the gas cylinders, CO delivery device, and measurements of COHb, SpCO, and ambient CO levels. Unblinded test results will be kept in a separate location from the blinded test results and concealed from the study coordinators.

The unblinded administering physician will be responsible for maintaining a separate password-protected limited-access project within the database with the subject identification number and CO-related measurements (SpCO, COHb, ambient CO) which the study coordinator will not have access to. While the administering investigator will be unblinded throughout the study due to safety monitoring, they will only be unblinded to the treatment assignment for subjects enrolled at their own site. Investigators will otherwise be blinded to the study treatment assignment for subjects enrolled at the other sites. Two lead RTs ([name] and [name]) may become unblinded to the treatment assignments at other sites to assist with study drug administration procedures if necessary.

If the clinical team believes that unblinding is medically necessary in order to properly treat the patient, the unblinded administering physician can disclose study product assignment. If there is time to do so, the unblinded administering physician should discuss this unblinding with the unblinded DCC physician prior to the disclosure. All episodes of unblinding, whether deliberate or inadvertent, will be reported to the DSMB at the next routine report.

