9.3.1 ASSIGNING A RANDOMIZATION

All subjects will be randomized through the StudyTRAX database using a permuted block method with random block sizes. The unblinded physicians or RTs or blinded coordinators will randomize the subject after enrollment. Subjects will receive a Randomization ID (RI-SiteCode-Seq) which includes a Site Code and Sequence starting with 0001 per site (eg. RI-BWH-0001, RI-MGH-0001, RI-DUH-0001, RI-WCM-0001, RI-DVA-0001, RI-BMH-0001, RI-DRH-0001).

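### Section 9.3 places an unblinded coordinating-centre physician in the review of candidates before randomization, so allocation concealment is not fully protected at that step

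*Combined protocol and SAP*

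**What the plan says.** **Who reviews candidates.** Section 7.3 states: "Site investigators will review all potential study participants with one of the Data Coordinating Center (DCC) physician members". Section 9.3 repeats the requirement. In both, it comes before the sentence on consent and randomization. The last sentence of Section 9.3 then describes the step: "This central review of randomization by the DCC unblinded physician will ensure that no subjects are enrolled in this multi-center trial". The sentence goes on to name study holds as the situation to be prevented. Section 7.3 has no matching sentence, and neither section says whether every reviewing DCC physician is unblinded.

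**How patients are allocated.** Section 9.3.1: "All subjects will be randomized through the StudyTRAX database using a permuted block method with random block sizes". Section 9.3: "The randomization ratio will be 1:1 iCO:placebo". Section 7.3: "The randomization will not be stratified by any factors". The block sizes are not given.

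**What others may know.** Administering investigators know assignments at their own site. Section 7.3 adds: "Investigators will otherwise be blinded to the study treatment assignment for subjects enrolled at the other sites". Two lead respiratory therapists are named as possible exceptions.

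**The concern.** The reviewer acts before assignment, is described as unblinded, and has a stated task (preventing entry during a hold) that needs no knowledge of treatment. In a 1:1 permuted-block list, a person who knows the earlier assignments can see which arm is behind in the running block and guess the next one better than chance.

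There is some room for such a guess to matter. Several criteria in Sections 6.1 and 6.2 call for judgement: expected survival, commitment to full support, severity of inhalational injury, and whether cardiac failure explains the respiratory failure. The 168-hour window in Section 6.3 and the rescreening rule in Section 6.4 make it possible to put off an entry.

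Selection at entry is not undone by later blinding of coordinators, X-ray readers or the ICU team. With 16 patients per arm and no stratification, a few steered entries could shift baseline severity or mtDNA between arms.

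**Working it through.** The plan states no predictability figure, so there is none to reproduce. The check has two parts.

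**1. What might the reviewer know?**

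Pointing towards knowledge across sites:
- Section 7.3 makes the unblinded DCC physician the person to consult before an emergency disclosure, with no limit by site.
- Section 7.4 has the DCC review forms on which staff record the assignment.
- Section 11.1.6 has DCC physician members help prepare the DSMB and adverse event reports. It does not say that these show assignments.

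Pointing the other way:
- Section 7.3 names only the two lead therapists as possible exceptions to cross-site blinding, and access to the limited-access project needs the PI's permission.
- Section 9.2.1 runs the sites as separate database projects, with own-site access unless further privileges are granted.

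The text does not settle the question, so both cases are computed.

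**2. How well could the next assignment be guessed?**

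Inputs from the plan: N = 32, ratio 1:1, random block sizes, and seven sites. One list for all sites is inferred from the absence of stratification. Assumptions: the block-size sets, equal probability for each size, and a guesser who knows the possible sizes but not the block boundaries.

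Let (a, c) be the iCO and placebo places left in the current block, and w(a, c) the guesser's probability for that state. Then:

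- p = P(next is iCO) = Σ w(a, c) × a / (a + c)
- chance of a correct guess = max(p, 1 − p)
- the assignment is certain if p is 0 or 1

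The weights are updated after each assignment the guesser sees. Results are averaged over 32 positions in 1,500 simulated lists per scenario.

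*Hand check, fixed and known blocks of 4.* The chances of a correct guess at the four positions are 1/2, 2/3, 2/3 and 1, with mean 2.833/4 = 70.8%. The certain share is (0 + 0 + 1/3 + 1)/4 = 33.3%. The simulation gives 70.8% and 33.3%.

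*All earlier assignments known, random blocks:*

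| Assumed sizes | Correct | Extra correct among 32 | Certain | Certain among 32 |
|---|---|---|---|---|
| 2/4 | 72.0% | 0.220 × 32 = 7.0 | 10.8% | 3.5 |
| 2/4/6 | 69.9% | 0.199 × 32 = 6.4 | 3.9% | 1.2 |
| 4/6 | 68.7% | 0.187 × 32 = 6.0 | 5.5% | 1.8 |
| 4/6/8 | 67.5% | 0.175 × 32 = 5.6 | 2.3% | 0.7 |

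A simpler rule gives nearly the same rates: guess whichever arm is behind so far, and toss a coin when the arms are level. Over 8,000 lists it was right 72.0%, 69.9%, 68.8% and 67.5% of the time, in the same order. That rule needs no knowledge of block sizes, so hiding the sizes would not by itself remove the advantage.

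*One site's assignments known (a random 1/7 of the list):* 53.3%, 53.1%, 53.0% and 52.9% correct, and essentially none certain. The gain is about 0.03 × 32 = 1 extra correct guess.

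*No earlier assignments known:* 50%, none certain.

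**The case against.** A reader might infer that the reviewer can predict the next assignment and that allocation concealment fails. The documents do not support that reading, for these reasons:

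- **Random block sizes.** Sections 7.3, 9.3 and 9.3.1 all specify them. Even a person who saw every earlier assignment would be certain of only about 1 to 3.5 of 32. The assignment is made in StudyTRAX after consent and viewed only afterwards.
- **Knowledge across sites is not stated.** The roles section (11.1.5) was not available and may limit it. Its absence from the review copy is not a gap in the plan. If the reviewer knows one site only, almost nothing is gained.
- **No veto is stated beyond study holds.** Eligibility rests on listed criteria and is reviewed with the site PI or designee, and entry also needs the attending physician's permission and consent.
- **Not stratifying helps against site staff.** They see only their own part of one shared list. It is a weakness only for someone unblinded across sites.
- **Adjustment is planned.** Section 10.4.2 includes a repeated-measures ANCOVA with baseline values, age and ARDS severity.

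The first four points stand and limit the size of the problem. The fifth stands in part: the Mann-Whitney comparison of change in the same section is unadjusted, and adjustment cannot correct for unmeasured features on which patients were selected. None of them explains why a check for study holds should be made by someone unblinded.

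**Conclusion.** The point holds in a limited form. Section 9.3 describes the central reviewer of candidates as unblinded, and the available text puts no barrier between that review and earlier assignments. Concealment is therefore not fully protected at this step.

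The upper figure, a correct-guess rate of about 67 to 72%, is a worst case. It assumes that the reviewer sees assignments at all sites, that one list serves all sites, and that block sizes resemble the sets tried. The one-site figure of about 53% is the mild case. These are guess rates. They do not measure bias in the mtDNA result, which would also require that the reviewer could, and did, influence who was entered. The documents show neither. This is an avoidable route to selection bias that is inexpensive to close, and not evidence that the randomization is compromised.

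**What to change.** In Sections 7.3 and 9.3:

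1. Assign the pre-randomization review to a DCC physician member who has no access to assignments, the limited-access project or by-arm reports. This is the main change. If practice already works this way, say so and reconcile the two descriptions of the reviewer.
2. Keep the unblinded DCC physician for safety and unblinding calls after randomization.
3. Enforce study holds by locking the StudyTRAX randomization tool.
4. Require eligibility to be signed off before the randomize function opens.
5. Withhold block sizes from anyone who screens or clears candidates. This limits certain predictions and supplements item 1 without replacing it.

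The cost is a reassignment among existing DCC physicians and a change of StudyTRAX settings. The drawback is slightly less flexible on-call cover for candidate review.

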9.3.1 ASSIGNING A RANDOMIZATION

All subjects will be randomized through the StudyTRAX database using a permuted block method with random block sizes. The unblinded physicians or RTs or blinded coordinators will randomize the subject after enrollment. Subjects will receive a Randomization ID (RI-SiteCode-Seq) which includes a Site Code and Sequence starting with 0001 per site (eg. RI-BWH-0001, RI-MGH-0001, RI-DUH-0001, RI-WCM-0001, RI-DVA-0001, RI-BMH-0001, RI-DRH-0001).

9.3.2 VENTILATOR PROCEDURES

FiO₂ will be increased prior to study drug administration in order to achieve a PaO₂ ≥ 80 or SpO₂ ≥ 95%. Ventilator management, including weaning, will follow the modified ARDS Network lower tidal volume (6 mL/kg PBW) protocol (**Appendix G**)⁹. If not already being utilized, this low tidal volume protocol for mechanical ventilation must be initiated within two hours of randomization. Since the time a patient achieves unassisted ventilation affects a secondary endpoint, VFDs, and because recent evidence-based consensus recommendations have identified a best practice for weaning, weaning strategy will also be controlled by protocol rules in accordance with these evidence-based recommendations. This newer weaning strategy is a simplified version of the protocolized weaning strategy used in prior ARDS Network studies (**Appendix G**). Study drug administration will be continued in patients undergoing weaning from mechanical ventilation as in **Appendix G** unless the subject is deemed ready for extubation by the clinical team.

9.4 REFERENCE MEASUREMENTS (DAYS 1 – 3)

Reference Measurements (Days 1 – 3)

The following parameters will be measured and recorded daily on study Days 1 through 3 from 3:00-10:00 am using the values closest to 8:00 am on the days specified in the **Time-Events Schedule (Section 1.3)**. On days when the study drug is administered, the ventilator parameters will be recorded using the values closest to the study drug administration. Details regarding the below assessments are found in **Section 9.1**.

The following conditions will be ensured prior to reference measurements:

- No endobronchial suctioning for 10 minutes
- No invasive procedures or ventilator changes for 30 minutes
- All vascular pressures will be zero-referenced to the mid-axillary line with the patient supine.

Reference Measurements

1. Vital Signs
2. CVP if available
3. EKG
4. Ventilator Parameters Assessment (closest to the time of study drug administration)
5. Frontal Chest Radiograph
6. Lung Injury Score (LIS)
7. SOFA Score
8. GCS
9. RASS

10. ScvO₂ if available
11. CBC
12. Basic metabolic panel if available and requested by treating physician
13. PT/PTT/INR if available and requested by treating physician
14. Serum CK, AST, ALT, Albumin, Total Protein if available and requested by treating physician
15. Bilirubin
16. Lactate
17. Vasopressors and Inotropes Review
18. Fluid intake, fluid output (most recent 24 hour value) or mean hourly value for most recently available period
19. Renal replacement therapy status
20. Concomitant Medications Review
21. Adverse Event Monitoring
22. Blood for Biomarker Collection
23. Urine Sample Collection
24. Microbiological results when available
25. Discarded BAL fluid and plasma if available

9.5 STUDY DRUG ADMINISTRATION ASSESSMENTS (DAY 1-3)

The following assessments will be done on Days 1 – 3 prior to study drug administration. **No treatment will be started before these assessments are performed and the pre-treatment checklist is completed by the study investigator**

Calibration of IL GEM Premier Co-oximeter and COventDS: Calibration will be performed according to device manuals and SOP. Documentation of calibration will be kept in study files.

COHb Level: The baseline COHb level will be drawn and assessed by an unblinded physician investigator, just prior (less than 15 minutes) to starting the study drug administration. COHb will be measured by study investigators using an IL GEM Premier Co-oximeter at the patient's bedside. These results are obtained within less than 5 minutes. The study drug will not be started until this result is obtained and reviewed for a potential study hold. All COHb level result printouts should be filed in the unblinded subject file.

Lactate Level: Lactate level will be measured and assessed daily by the local laboratory at each center prior to study drug administration. The study drug will not be started until this result is obtained and reviewed by the study physician investigator for a potential study hold.

Hemoglobin Level: Hemoglobin will be measured and assessed daily prior to study drug administration. The hemoglobin level will be measured by the local laboratory at each center. The study drug will not be started until this result is obtained and reviewed by the study physician investigator for a potential study hold.

EKG: A 12 lead EKG will be obtained and reviewed daily by the study staff physician prior to study drug administration to evaluate for cardiac exclusion criteria ie. acute MI, ACS, or unstable atrial or ventricular arrhythmia. The study drug will not be started until the EKG is obtained and reviewed by the study physician investigator for a potential study hold. The EKG will also be officially read locally at each site.

Review Ventilator Parameters: The study staff will record ventilator parameters prior to starting study drug administration.

Calculate Deadspace (Vd/Vt): Dead space fraction will be measured daily by the administering RT or physician prior to study drug administration using a NICO or NM3 monitor (Respironics) and the PCO₂ obtained from an arterial or venous blood gas.

Blood Gas Analysis (arterial or venous): Arterial or venous blood will be drawn for blood gas analysis by the local laboratory at each center. The blood gas will be assessed daily prior to starting study drug administration. The study drug will not be started until this result is obtained and reviewed by the study physician investigator for a potential study hold. The following values will be recorded from the ABG or VBG results: pH, PCO₂, PO₂, and base excess or deficit.

Monitor SpCO and SpO₂ with pulse oximeter: SpCO and SpO₂ will be measured prior to treatment, recorded at intervals as described below, and monitored throughout study drug treatment using a noninvasive pulse oximeter (Masimo Radical-7).

Ambient air CO levels: Ambient air CO levels will be measured before and throughout study drug treatment using a calibrated Dräger Pac 7000 CO detector. This will ensure that ambient levels are maintained within acceptable limits for occupational exposure.

Ensure blinding: All CO monitoring will be carried out by the unblinded administering RT and/or investigator and concealed from the blinded study team members.

Review for Adverse Events: The blinded study coordinator will review events over the past 24 hours that may meet criteria for adverse events.

9.5.1 REVIEW PARAMETERS PRIOR TO ADMINISTRATION OF STUDY DRUG

Review the Daily Hold Parameters (detailed information in **Section 7.1.6**). Administration of the study drug will be held if the following criteria are met.

Daily Hold Parameters:

- COHb level $\geq 3\%$
- Lactate ≥ 4 mmol/L
- ST elevation MI or unstable angina/non ST elevation MI concerning for ACS
- Unstable atrial or ventricular arrhythmia
- Severe hypoxemia defined as SpO₂ < 95 or PaO₂ < 90 on FiO₂ ≥ 0.9
- Hemoglobin < 7.0 g/dL
- Diffuse alveolar hemorrhage from vasculitis
- Use of high frequency ventilation
- Use of inhaled pulmonary vasodilator therapy (eg. NO or prostaglandins)
- Use of ECMO
- Occurrence of an AE meeting criteria for study drug hold or discontinuation (**Sections 7.1.6, 7.1.8.**).

9.5.2 STUDY DRUG ADMINISTRATION AND MONITORING

The study drug will be administered for up to 90 minutes daily for up to 3 days following randomization or until discontinuation of mechanical ventilation, whichever occurs first according to **Section 7.1.9**. See **Sections 7.1.6, 7.1.7, and 7.1.8** for information about study drug hold, interruption, and permanent discontinuation criteria.

Monitoring during Study Drug Administration:

Subjects will be monitored with continuous pulse oximetry, cardiac monitoring, and either intermittent (at least every 15 minutes) or continuous blood pressure monitoring (if an arterial line is in place) throughout the course of the 90 minute study drug treatment.

SpCO and SpO₂ will be monitored continuously using a Masimo Rad-7 non-invasive pulse oximeter, and recorded at the time points specified below. COHb levels will be measured using an IL GEM Premier Co-oximeter and recorded at the time points specified below. Arterial or venous blood will be drawn for blood gas analysis prior to treatment and at the completion of study drug administration (90 min or earlier if discontinued prior to 90 min). If study drug treatment is discontinued prior to 90 min, all of the scheduled 90-minute measurements will be made and recorded at the time of study drug discontinuation.

Ambient CO levels will be monitored continuously using a Dräger Pac 7000 CO detector, and recorded at the time points specified below.

	ABG or VBG (pH, PCO ₂ , PO ₂)	FiO ₂	COHb level (IL GEM Premier co-oximeter)	CFK look-up table (Appendix B or StudyTRAX)	SpCO (Masimo Rad-7)	SpO ₂ (Masimo Rad-7)	Ambient CO Level (Dräger Pac CO detector)
Pre-treatment	X	X	X		X	X	X
20 min			X	X	X	X	X
60 min			X		X	X	X
75 min			X		X	X	X
90 min*	X	X	X		X	X	X
180 min			X		X	X	X

*90 min or upon completion of study product if discontinued sooner than 90 min.

CFK Equation-Based Table: The unblinded administering physician and/or RT will use the CFK equation-based table (**Appendix B or electronic equivalent version in StudyTRAX**) to look up the time at which the COHb level is predicted to be 8%. If the CFK-equation predicted time is 90 min or greater, the study drug will be administered for 90 minutes. If the CFK-equation predicted time is less than 90 min, the study drug will be discontinued at the time the COHb level is predicted to be 8%. The required 90 minute measurements will be replaced by measurements done at the completion of the study drug administration if study product administration is discontinued prior to 90 min. Note that for FiO₂ > 55%, the COHb level will never reach 8% with administration of 200 ppm CO and therefore the study drug treatment should be administered for the complete 90 minutes.

